Nicotinamide riboside (NR) is a pyridine-nucleoside form of vitamin B3 that functions as a precursor to nicotinamide adenine dinucleotide or NAD⁺. Studies in mice have shown that boosting the levels of NAD⁺ can produce multiple health benefits, including reducing nerve damage (Trammell et al., 2016a; Hamity et al., 2017). In humans, the levels of NAD⁺ diminish with age and it has been suggested that loss of this metabolite may play a role in age-related health decline (Johnson and Imai, 2018). NR is FDA approved as a dietary supplement and can be purchased over the counter.

4. Study Procedures

a. Study design:

This is a randomized double-blinded study to evaluate the effects of NR on experimental axon degeneration and regeneration. After the initial screening (visit 1) is completed, the patients will undergo a skin biopsy and be randomized to either the study drug or placebo and will be instructed to take it for a week prior to visit 2. Based on existing pharmacokinetic studies, this should be sufficient to raise the plasma NAD levels at the time of experimental denervation of the skin. At visit 2, patients will undergo two baseline skin biopsies and application of the capsaicin patch for 48 hours and will be instructed to continue the study drug. At visit 3 (48 hours after visit 2), capsaicin patch will be removed, and a repeat skin biopsy will be done to evaluate the degree of epidermal denervation. Patients will be instructed to continue the study drug for another 3 months and will undergo repeat skin biopsies at 2 months (visit 4) and 3

months (visit 5). Blood samples will also be drawn at each visit to measure NAD levels to confirm compliance and to correlate with degree of epidermal innervation. Figure 1 depicts a schema of visits and timelines.

b. *Study duration and number of study visits required of research participants.*

As outlined above, there will be a total of 5 visits over 3 and ½ months.

c. *Blinding, including justification for blinding or not blinding the trial, if applicable.*

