- Abnormal Labs: HIV, B12, HgA1c, Thyroid Stimulating Hormone (TSH), Complete Blood Count (CBC), Comprehensive Metabolic Panel (CMP)

6. Drugs/ Substances/ Devices

- a. *The rationale for choosing the drug and dose or for choosing the device to be used.*

As outlined in background section NR is commercially available as a nutritional supplement and has been evaluated in humans in a Phase 1 pharmacokinetic study (Trammell et al., 2016b). It is safe at the doses used in that study (100 mg, 300 mg and 1000 mg) over the course of 36 days with no significant side effects except 2 patients reporting flushing sensation. Since NR is able to elevate the NAD levels in plasma, we expect that this correlates with elevated tissue levels of NAD and able to prevent distal axonal degeneration of small unmyelinated fibers induced by capsaicin.

- b. *Justification and safety information if FDA approved drugs will be administered for non-FDA approved indications or if doses or routes of administration or participant populations are changed.*

NR is available over the counter as a nutritional supplement as a form of vitamin B3 and is sold under various brand names including Tru Niagen at a dose of 300 mg per capsule. It is FDA approved as a nutritional supplement and recommended daily dose is 15 mg. However, based on the study by Trammell and colleagues, effect of NR on NAD metabolism was best observed at the highest dose of 1000 mg/day. There were no significant side effects or toxicity at that dose over 36 days of observation. Furthermore, a more recent clinical trial of NR in obese men looked at the effects of NR on insulin sensitivity over 12 weeks and utilized a dose of 1000 mg twice a day without any significant side effects or drop out from the study (Dollerup et al., 2018). In this study there were increases in multiple NAD metabolites in the serum and urine with this dose. Given that both studies did not observe any side effects or toxicity doses above 1000 mg a day, and that the study by Dollerup and colleagues showed increases in NAD metabolites, we plan to use 1000 mg orally (four 250mg capsules) twice a day for convenience

Date: March 25, 2019

Principal Investigator: [name]

Application Number: IRB00210072

of dosing using the commercially available NR. The placebo capsules will be prepared by ChromaDex who is also supplying the study drug.

- c. *Justification and safety information if non-FDA approved drugs without an IND will be administered.*

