The study will be terminated early if the subjects experience any significant side effects. NR is produced as a supplement by a number of different manufacturers. There have been no side effects reported. Additionally, it was well tolerated in several published studies. Therefore we do not anticipate any toxicity. If a subject complains of side effects, the potential for any causation will be reviewed by Drs. [name] and [name] and reported to the IRB.

8. Risks

Date: March 25, 2019

Principal Investigator: [name]

Application Number: IRB00210072

a. *Medical risks, listing all procedures, their major and minor risks and expected frequency.*

The capsaicin denervation model and other study procedures have been successfully performed in numerous Johns Hopkins IRB-approved studies (including as part of six industry-sponsored multicenter clinical trials with over 600 subjects total. Therefore, we do not anticipate any complications.

Neurological exam: There are no risks associated with a neurological examination.

Capsaicin cream: Capsaicin is the active ingredient in hot peppers and may cause a local burning sensation to the area that it is applied. The degree of burning is generally less than mild sunburn. The affected area will become less sensitive to sensory stimuli due to local nerve fiber degeneration. With time the area should return to normal or near normal with subsequent nerve regeneration and reinnervation of the skin. We have obtained IRB approval for similar studies in the past (RPN00-10-25-01, RPN 99-11-02-01, NA_00010088 (multicenter trial), WIRB Pr. No.: 20060008 (multicenter trial)) and have a FDA exemption letter for the use of topical capsaicin. The study participants may use over-the-counter, non-steroidal pain medications to manage any pain associated with the use of capsaicin cream.

Skin biopsy testing requires taking a 3mm-punch biopsy. The affected areas are anesthetized with subcutaneous 1% lidocaine with epinephrine, and the site will be sterilely dressed after the procedure. No sutures are involved. The patients will receive instructions how to care for each biopsy site after the procedure. The risk of infection is estimated at 1:500 and is likely less in healthy subjects. Punch skin biopsy may result in a small scar that generally fades by one year.

b. *Steps taken to minimize the risks.*

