The skin biopsies will be done under sterile conditions. Patients will be given clear instructions on how to care for the biopsy sites.

c. *Plan for reporting unanticipated problems or study deviations.*

If the patients experience any signs of infection at the site of biopsies, they will be asked to call the study coordinator and/or principal investigator. They will be seen in the clinic and appropriate medical care will be provided. Similarly, if the patients experience any side effects from the study drug, they will be asked to call the study coordinator and/or the principal investigator and report it.

d. *Legal risks such as the risks that would be associated with breach of confidentiality.*

In order to preserve participant confidentiality, all study participant records will be stored in a locked file cabinet located in the study coordinator's office. All subjects will be given a study-specific unique identifying number and this will be used to label study documents. Data spreadsheets will use deidentified subject study numbers and will be password protected and stored on the study coordinator's computer which is backed up regularly.

e. *Financial risks to the participants.*

There is no cost to participate in the study.

9. Benefits

Date: March 25, 2019

Principal Investigator: [name]

Application Number: IRB00210072

There is no direct benefit to subjects. We are testing the potential benefit of NR on human nerve degeneration and regeneration.

10. Payment and Remuneration

There will be no cost to study subjects to participate. Subjects will be paid \$100/session for each study visit (\$500 total) plus \$100 if they complete all 5 visits of the study. Each subject will be paid \$300 after the 3rd visit and the remaining \$300 at the completion of the 5th visit. If subjects decide not to continue with the study, they will be paid for the sessions they completed but they will not be eligible to receive the study completion bonus of \$100.

11. Costs

- a. There is no cost to participate in the study.

12. References

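### Side effects are described as becoming known only when a participant calls or complains, so mild ones such as flushing may be under-counted at 2000 mg/day

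*Combined protocol and SAP*

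**What the plan says.** Two places state how a side effect of the study drug comes to the team's attention. Section 8c: "if the patients experience any side effects from the study drug, they will be asked to call the study coordinator" or the principal investigator. Section 7d: "If a subject complains of side effects, the potential for any causation will be reviewed" and passed to the IRB. Section 7d also ends the study early for significant side effects, without defining the term.

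Section 4a describes the visits: skin biopsies, the capsaicin patch going on and coming off, drug instructions, and blood. The purpose given for the blood is NAD: "Blood samples will also be drawn at each visit to measure NAD levels to confirm compliance", and correlation with innervation. Sections 7a and 7b name epidermal nerve fiber counts and plasma NAD as outcomes. No safety outcome is listed.

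On prior safety, section 6a says of the Phase 1 study: "It is safe at the doses used in that study (100 mg, 300 mg and 1000 mg) over the course of 36 days". For tolerability, the same sentence records "no significant side effects except 2 patients reporting flushing sensation". Section 6b says that its effect on NAD metabolism "was best observed at the highest dose of 1000 mg/day", and that the later 12-week trial in obese men "utilized a dose of 1000 mg twice a day without any significant side effects or drop out from the study". It then supports the chosen dose by saying that "both studies did not observe any side effects or toxicity doses above 1000 mg a day". Section 7d states that no side effects of NR are on record.

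**The concern.** If the team learns of side effects only when a participant speaks up, the record depends on what participants think worth mentioning. A healthy volunteer is more likely to let a brief, mild symptom pass than a serious one. Flushing is that kind of symptom, and it is the only NR effect that the protocol itself reports. At stake is how well this placebo-controlled trial can describe tolerability at 2000 mg/day: a low flushing count could mean little flushing or little reporting.

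The sentence in 6b adds to this. It makes the safety experience above 1000 mg/day look like two studies when the same section shows one. Together with the statement in 7d, it also leaves flushing out of view in the places where a reader would look for reasons to ask about it.

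**Working it through.** **Collection route, section by section**

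| Section | What it describes | Who starts it |
|---|---|---|
| 8c | Call to coordinator or investigator | Participant |
| 7d | Causation review after a complaint | Participant |
| 4a | Biopsies, patch, drug instructions, blood for NAD | Staff, but no side-effect question named |
| 7a, 7b | Nerve fiber counts, plasma NAD | No safety item |

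By 4a, the drug is started after visit 1 and taken for a week before visit 2. Visits 2, 3, 4 and 5 therefore all fall after dosing starts. The text names a side-effect question at none of these four.

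**Doses, from 6a and 6b**

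- This trial: 4 capsules × 250 mg = 1000 mg; × 2 per day = 2000 mg/day.
- Phase 1 study: 100, 300 and 1000 mg; the highest is given as 1000 mg/day.
- 12-week trial: 1000 mg × 2 = 2000 mg/day.
- Ratio of this trial's dose to the Phase 1 maximum: 2000 / 1000 = 2.
- Studies above 1000 mg/day: as 6b reads, 2 of 2; from the doses it lists, 1 of 2.

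The Phase 1 study could not have seen side effects above 1000 mg/day, because it tested nothing there.

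**Flushing.** Section 6a reports it in 2 participants. Read plainly, 6b says that neither study saw any side effect, and 7d says that none have been reported. Both conflict with 6a. The protocol does not say at which dose the flushing occurred. Nor does it give the size of the Phase 1 study, so no flushing rate can be derived.

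**Size of the under-count.** With 20 participants on NR, the expected number of recorded cases is 20 × (true rate) × (share reported). The documents give neither the rate nor the share, so no figure is offered.

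**What a table by arm could show.** With 20 per arm and no placebo cases, the two-sided Fisher p-value for k cases against 0 is 2 × C(20,k) / C(40,k).

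- k = 4: 2 × 4,845 / 91,390 = 0.106
- k = 5: 2 × 15,504 / 658,008 = 0.047

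It would take 5 against 0 to fall below 0.05, so the table should be descriptive.

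**Workload of asking everyone.** 40 participants × 4 visits = 160 questionings. At an assumed 2 to 3 minutes each, that is 320 to 480 minutes, or 5.3 to 8.0 hours in total.

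**The case against.** The collection point argues from silence in a short IRB form. Section 8c covers reporting of problems and deviations and is not written as an adverse-event procedure. The visit schema (Figure 1) and the consent pages were not available for this check and could contain a visit item. A complaint under 7d need not be a phone call, since participants meet staff face to face four times after dosing starts, twice within about nine days. This stands as a limit: the point concerns what the available text describes, and staff questioning is not excluded.

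It can also be said that no planned conclusion suffers. The hypotheses and outcomes concern nerve fibers and NAD, and no tolerability rate is promised. That is correct, and it is why this is only a suggested improvement.

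The 6b sentence is ungrammatical and may have been meant to say at or above 1000 mg. The true doses of both studies stand in the same section. Even on that looser reading, two studies are counted where one tested the planned dose, and the flushing conflict remains. Still, this is a wording correction that would not merit a point alone.

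A reader might go further and infer that 2000 mg/day lacks safety support. The documents do not say so: the 12-week trial used exactly that dose and is described as free of significant side effects and drop-out. A reader might also infer that the Phase 1 participants took 1000 mg daily for 36 days. The protocol supports only observation over 36 days and does not say how the three doses were arranged.

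**Conclusion.** The concern holds as a modest one. In the available text, drug side effects come to light only through a participant's call or complaint, and none of the four visits after dosing starts has a described side-effect question. Mild effects such as flushing may therefore be under-counted at 2000 mg/day. This rests on the judgement that mild symptoms are volunteered less often than they are admitted when asked. The documents do not measure that, and the shortfall cannot be quantified from them.

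Two stronger readings are tempting and unsupported. One is that the stopping rule in 7d would fail; it turns on significant effects, which participants would mostly volunteer, so little harm is shown. The other is that the trial's results are compromised; the nerve fiber and NAD analyses do not use side-effect reports and are unaffected.

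The accompanying inconsistencies are certain but small: one of the two cited studies, not both, went above 1000 mg/day, and 7d and 6b disagree with the flushing reported in 6a. Neither changes the dose or any analysis.

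**What to change.** Keep call-in reporting and add the following.

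- At existing visits 2 to 5, the clinical team asks every participant one standard question: any new symptom since the last visit, and flushing yes or no. At visit 3, flushing is asked about away from the capsaicin patch, because 8a says that the cream can burn locally.
- Tabulate the answers descriptively by arm after the code is broken. Do not pass them to the nerve laboratory.
- Reword 6b to say that the Phase 1 study's highest dose was 1000 mg/day, observed over 36 days, with 2 flushing reports at an unstated dose, and that only the 12-week trial tested 2000 mg/day.
- Change the statement in 7d so that it agrees with 6a.

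The cost is the few staff hours worked out above, one small table and two text edits, with no new visit, sample or dose change. There are three downsides. More unrelated minor complaints will be recorded, so the placebo column is needed to read the NR column. A flushing answer may hint at the arm to clinical staff, although the laboratory reading the biopsies stays blind under 4c. Recall will also be weaker at visit 4, about two months after visit 3, so call-in reporting still matters there.
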